10. CLINICAL MONITORING

Site monitoring is conducted to ensure that the human subject protections, study and laboratory procedures, study intervention administration, and data collection processes are of high quality and meet sponsor, ICH/GCP guidelines and applicable regulations, and that the study is conducted in accordance with the protocol, protocol-specific MOP and applicable sponsor standard operating procedures. DMID, the sponsoring agency, or its designee will conduct site-monitoring visits as detailed in the clinical monitoring plan.

Site visits will be made at standard intervals as defined by DMID and may be made more frequently as directed by DMID. Monitoring visits will include, but are not limited to, review of regulatory files, accountability records, eCRFs, informed consent forms, medical and laboratory reports, and protocol and GCP compliance. Site monitors will have access to the study site, study personnel, and all study documentation according to the DMID-approved site monitoring plan. Study monitors will meet with site principal investigators to discuss any problems and actions to be taken and document visit findings and discussions.

11. STATISTICAL CONSIDERATIONS

11.1. Study Hypotheses

The primary objective of the study is to assess the clinical response of early empiric antifungal therapy with fluconazole at Day 22 in subjects with coccidioidomycosis pneumonia.

The study is designed to test the following hypothesis in the primary efficacy analysis conducted in the cocci-positive per protocol analysis population (see Section 11.4.1):

Null hypothesis: “The proportion of subjects with coccidioidomycosis pneumonia with protocol-defined clinical response is the same in the cohort of subjects receiving fluconazole as compared to placebo.”

Alternative hypothesis: “The proportion of subjects with coccidioidomycosis pneumonia with protocol-defined clinical response is different in the cohort of subjects receiving fluconazole as compared to placebo.”

The study design and primary hypothesis is based on the following parameters supplied by subject matter experts:

- The composite score will be sensitive to changes in the course of disease as a result of empiric treatment with fluconazole.
- A 50% reduction in composite score is a clinically meaningful reduction which has been used as a measure of clinical response in other trials.
- A Day 22 time point will be optimal for measuring clinical response as compared to a longer time point because subjects in both study arms will eventually resolve disease,
- The proportion of subjects responding at Day 22 will be 0.20 and 0.40 in the placebo and fluconazole arms, respectively.

However, there is considerable uncertainty in the design parameters, as they are based on natural history studies, and this is the first randomized trial of empiric therapy with fluconazole for coccidioidomycosis. The most important contribution of this trial may be to confirm or refute these assumptions and set the stage for future trials.

Several of the secondary and exploratory objectives in the trial are focused on validating the sensitivity of the composite score, and its individual components, to intervention with fluconazole. This is motivated by Blair et al. (2014) who reported that subjects who received antifungal treatment had a reduced time to full attendance at work and reduced time to 50% improvement in SF-36 Physical Component Score [13].

11.2. Sample Size Considerations

11.2.1. Sample Size for Per Protocol Analysis Population

The primary analysis will compare the proportion of subjects achieving clinical response at Day 22 among efficacy evaluable subjects, defined as subjects in the Cocci-Positive Per Protocol analysis population who meet the case definition of coccidioidomycosis pneumonia who were compliant with the intervention administration and have coccidioidal serology data available at the Day 1 and 22 visits. We further assume that the clinical response proportion at Day 22 will be 0.20 in the placebo arm, and 0.40 in the fluconazole arm. As described in section 11.2.3, enrollment will continue until 200 subjects are evaluable for efficacy, 100 in each treatment arm, which suffices for 88% power for the Z test with unpooled variance to compare proportion of clinical responses at Day 22 at the two-sided level of 0.05. This is the primary sample size calculation which forms the basis for target enrollment to the study and for subsequent sample size re-estimation procedures at scheduled interim analyses while the study is enrolling.

A secondary analysis in the Cocci Positive Modified Intent-to-Treat population will compare the proportion of responders at Day 22, treating subjects dropping out before the Day 22 visit as non-responders. Assuming that the probability of drop-out before Day 22 is 20% among cocci-positive subjects, we would expect that 250 cocci-positive subjects would be available for this secondary analysis as a result of reaching the target sample size of 200 cocci-positive subjects with Day 22 follow-up for the primary analysis. Since subjects who drop-out are considered non-responders, the probability of response in the control-arm subjects would be $0.8 * 0.2 = 0.16$, and in the treated subjects would be $0.8 * 0.4 = 0.32$. The Z-test with unpooled variance has power of 85% to detect this difference in response proportions with 125 cocci-positive subjects per arm.

A secondary analysis in the Intent-to-Treat population will compare the proportion of responders at Day 22 between fluconazole and control arms in all randomized subjects, using a two-sided level .05 test of non-inferiority with a margin of an absolute difference of 0.05. Subjects who drop-out before Day 22 will be imputed as non-responders for cocci-positive subjects, and as responders for cocci-negative subjects. Assuming that an enrolled subject has a 20% chance of being cocci-positive, and that the probability of response is 20% among cocci-positive subjects receiving control, 40% for cocci-positive subjects receiving treatment, and 70% for cocci-negative subjects, then the probability that a control subject responds is given by $0.2*(0.8*0.2 + 0.2*0.0) + 0.8*(0.8*0.7 + 0.2*1.0) = 0.64$, and the probability that a treated subject responds is given by $0.2*(0.8*0.4 + 0.2*0.0) + 0.8*(0.8*0.7 + 0.2*1.0) = 0.672$. The non-inferiority test has power of 78% if 1,000 subjects are enrolled, and 86% if 1,250 subjects are enrolled.

The power calculations in this section were performed with PROC POWER in SAS 9.4 or in R.

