3.1.2. Secondary

- To assess the clinical response of early empiric antifungal therapy with fluconazole at Day 22 in subjects with coccidioidomycosis pneumonia regardless of adherence with the study intervention.
- To assess the clinical response of early empiric antifungal therapy with fluconazole at Day 43 in subjects with coccidioidomycosis pneumonia regardless of adherence with the study intervention.
- To compare the clinical response and its individual components over time, by treatment group, in subjects with coccidioidomycosis pneumonia.
- To assess the impact of early empiric antifungal therapy with fluconazole on days lost from work or school and responses to the SF-12v2 and PROMIS Item Bank v2.0 - Ability to Participate in Social Roles and Activities - Short Form 4a in subjects with coccidioidomycosis pneumonia.
- To assess the effect of early empiric antifungal therapy with fluconazole through Day 43 in subjects with coccidioidomycosis pneumonia on all-cause mortality by treatment group.
- To assess whether early empiric antifungal therapy with fluconazole at Day 22 is non-inferior to placebo as defined by clinical response at Day 22 in all randomized subjects, regardless of coccidioidomycosis pneumonia status or adherence with study intervention, with baseline and follow-up FLEET-CAP scores.

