5.3.4. Handling of Withdrawals and Discontinuation of Administration

The primary reason for withdrawal from the study will be recorded on the Study Status data collection form. Subjects will be encouraged to complete the Early Termination Visit. The Early Termination Visit procedures are listed in Section 7.6. Although subjects are free to withdraw at any time or may be withdrawn by the site principal investigator or appropriate sub-investigator at any time, subjects who receive at least one dose of the study drug will be encouraged to remain in the study for follow-up safety assessments and collection of clinical outcome data. Every attempt will be made to follow all serious adverse events ongoing at the time of early withdrawal to resolution.

In the case of subjects who fail to appear for a follow-up safety assessment, extensive effort (i.e., three documented contact attempts via phone calls, e-mails, etc., made on separate occasions and

followed by a certified letter) will be made to locate or recall them, or at least to determine their health status. These efforts will be documented in the subject's records.

See the appropriate section of the Manual of Procedures (MOP) for alternate follow-up requirements.

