7.4. Early Termination Visit (if needed)

7.4.1. Before Follow-up Visit 04

The following assessments will be performed at the early termination visit for subjects who withdraw, or are withdrawn or terminated from this study:

- Obtain interim medical/surgical history, including an assessment for new medical conditions and symptoms by interview of subjects and review of the medical record and note any changes since the previous visit.
- Record all concomitant medications on the appropriate data collection form.
- Assess any SAEs and record on SAE form and in AdvantageEDC.
- Complete a targeted physical examination based on symptoms.
- Record vital sign measurements (sitting blood pressure, sitting heart rate, respiratory rate, oral temperature, oxygen saturation and weight).
- Perform urine pregnancy test for women of child-bearing potential.
- Perform a 12-lead ECG if termination occurs before Day 15
- Perform a pill count of study product (fluconazole or placebo) and interview to determine adherence. Following pill count, collect the pill bottle and retain until study product accountability has been completed by the study monitor.
- Complete symptom Assessment including FLEET CAP Score, PROMIS Item Bank v2.0 - Ability to Participate in Social Roles and Activities - Short Form 4a, Extra-Pulmonary Symptom Score and SF-12v2
- Collect the number of days missed from school and/or work due to illness for subjects who were either enrolled in school or employed at baseline.
- Draw venous blood samples for the following:

-
- Safety laboratories (Hepatic function panel (AST, ALT, Alkaline phosphatase and total bilirubin), BUN, Creatinine) [10 mL]
 - Coccidioidal serologies (CF; qualitative IDCF and IDTP; EIA-IgM; EIA IgG; and quantitative IDCF) [15 mL]
 - Quantitative fluconazole level [5 mL]
 - Blood to be banked for future use [15 mL]
 - Contact subject with results of the safety lab testing for follow-up with health care provider if abnormalities are noted.
 - All available coccidioidal serologic results will be made available to the subject. The treatment status will be revealed to the participant. All participants will be invited to remain in study follow-up. Refer subject to their identified health care provider.

7.4.2. After Follow-up Visit 04 A telephone visit will be conducted.

The following assessments will be performed at the early termination visit for subjects who withdraw, or are withdrawn or terminated from this study:

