At the screening visit a physical examination will be performed by a clinician licensed to make medical diagnoses. A standard of care physical exam completed by a clinical provider within the 72 hours prior to screening may be used for the screening exam if all appropriate organ systems are examined and documented. The comprehensive physical examination must include the following organ or body system assessments: skin; head, eyes, ears, nose, and throat; thyroid; neurological; chest and lungs; cardiovascular; abdomen (liver and spleen); lymph nodes; musculoskeletal, genitourinary and extremities. Assessments of any specific signs or symptoms reported by the subject must also be performed and documented. Findings from the screening must be characterized as either normal or abnormal, and if abnormal, a description of the abnormality must be provided. Following the screening visit physical examination, targeted physical exams will be performed on Days 22, 29, and 43 if indicated based the subject's interim

medical history, and changes must be classified as new, worsened, or improved from those at screening.

Vital signs (sitting heart rate, sitting blood pressure (mmHg), respiratory rate, oral temperature (°C), oxygen saturation (SpO₂)) and weight will be collected at the screening visit, Days 22, 29, and 43. Vital signs assessed on Day 1 will be considered as baseline. Subjects must not eat anything hot or cold or smoke within 10 minutes prior to taking oral temperature. Height will be collected on Day 1.

A resting 12-lead ECG will be performed at Day 1 or the pre-screening visit and at early termination visits when applicable. An ECG completed as part of standard of care within the past 72 hours and that is available to the study team at the time of screening can serve as the screening ECG and does not require repeating. The ECG will be assessed for QT prolongation as well as other abnormalities indicative of QT prolongation while the subject is on-site for their study-related visit by a clinician licensed to make medical diagnoses.

The FLEET CAP score is an efficacy outcome measure based on a clinical scoring system that allows a constellation of clinical symptoms to be quantified and scored over time: cough, fatigue, chest pain, dyspnea, sputum production, night sweats, fever, and hypoxia. The FLEET CAP score will be completed on Days 1, 22, 29, and 43.

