11.4. Final Analysis Plan

11.4.1. Analysis Populations

Safety Analyses:

- Safety population – This safety analysis population includes all subjects who took at least one dose of study medication.

Efficacy Analyses:

- Intent-to-Treat (ITT) population – This efficacy analysis population includes all randomized subjects.
- Cocci Positive Modified Intent-to-Treat (mITT) population – This efficacy analysis population includes all randomized subjects who meet the case definition of coccidioidomycosis pneumonia and took at least one dose of study medication. Note that it is not necessary for a subject to be adherent to study drug to be eligible for inclusion in the mITT population.
- All Randomized Modified Intent-to-Treat (mITT) population – This efficacy analysis population includes all randomized subjects who took at least one dose of study medication regardless of cocci-status. Note that it is not necessary for a subject to be adherent to study drug to be eligible for inclusion in the mITT population.

- Cocci Positive Per-Protocol (PP) population – This efficacy analysis population includes randomized subjects who meet the case definition of coccidioidomycosis pneumonia who were compliant with the intervention administration and have coccidioidal serology data available at the Day 1 and 22 visits.
- All Randomized Per-Protocol (PP) population – This efficacy analysis population includes randomized subjects who were compliant with the intervention administration regardless of cocci-status and have coccidioidal serology data available at the Day 1 and 22 visits.

Adherence is assessed at each study visit depending on the fraction of expected pills taken on or before that time point. If at any visit the subject's cumulative fraction of pills taken drops below 80%, they are deemed non-adherent. This decision is not reversible, even if the subject's cumulative fraction of pills taken rises above 80% at a future visit.

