11.4.4.1. Primary Efficacy Analysis

The primary efficacy analysis tests the difference between the fluconazole and placebo treatment groups in the proportion of subjects with an occurrence of clinical response at Day 22. Subjects without a clinical response at Day 22 will be coded as treatment failures while subjects with a clinical response at Day 22 will be coded as an observed event if the clinical response outcome measure definition (Section 3.2.1) is met.

A test of difference between the proportion of clinical responses in the fluconazole and placebo groups at the Day 22 time point will be performed using the Z test. The use of this test statistic will permit us to use the method of B-values to calculate conditional power of the test in the planned futility analyses, as outlined in “Statistical Monitoring of Clinical Trials, a Unified Approach”, by Proschan et al [22]. Details of this procedure will be provided in the statistical analysis plan.

The primary efficacy analysis will be performed in the cocci-positive per protocol analysis population. Secondary analyses will be performed in the all randomized per protocol population, all randomized and cocci-positive ITT and the mITT populations (see also Secondary Objectives 1 and 6). Sensitivity analyses, which will assess the impact of drop-out, censoring mechanisms, and analysis methods on the primary analysis, may be performed. These analyses will be specified in the separate statistical analysis plan document.

In addition to the planned tests of hypotheses, descriptive analyses will be performed for the primary endpoint. The number of clinical responses observed will be tabulated by time point, including and beyond Day 22, and treatment group. Tabular and graphical summaries will be prepared for the composite MSG score across all assessment time points.

To investigate whether there is evidence of a differential diagnosis of coccidioidomycosis between treatment arms, which might result in selection bias for inclusion in our primary analysis, the number of coccidioidomycosis cases in each treatment arm will be compared among all randomized subjects.

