11.4.4.2. Secondary Efficacy Analyses

Table 11 below briefly outlines the analytic approaches that will be taken for the secondary efficacy analyses. Details of the analyses will be described in the separate statistical analysis plan document.

Table 11: Secondary Efficacy Analyses

Secondary Objective	Outcome Measure	Main Analytic Strategy
(SO 1): To assess the clinical response of early empiric antifungal therapy with fluconazole at Day 22 in subjects with coccidioidomycosis pneumonia regardless of adherence with the study intervention.	Proportion of clinical response at Day 22 regardless of adherence to the study intervention in each treatment group.	Repeat the primary efficacy analyses in the all randomized mITT, cocci-positive mITT, and ITT populations.
(SO 2): To assess the clinical response of early empiric antifungal therapy with fluconazole at Day 43 in subjects with coccidioidomycosis pneumonia regardless to adherence with the study intervention.	Proportion of clinical response at Day 43 regardless of adherence to the study intervention in each treatment group.	Repeat the analyses for SO 1 using Day 43 as the time point for the outcome measure instead of Day 22 as well as perform a time-to-event analysis. This analysis will be performed in the all-randomized mITT, cocci-positive mITT, and ITT populations.

(SO 3): To compare the clinical response and its individual components by study group, over time, in subjects with coccidioidomycosis pneumonia.
	
The mean, median, and quartiles of the FLEET CAP score at Days 22, 29 and 43 in each treatment group.
 
The mean, median, and quartiles for each component of the FLEET CAP score at Days 22, 29 and 43 in each treatment group.
 
 1. Cough 2. Fatigue 3. Chest Pain 4. Dyspnea (Shortness of breath) 5. Sputum production 6. Night Sweats 7. Fever 8. Hypoxia 	
Descriptive and/or graphical summaries of the outcome measures by treatment group. This analysis will be performed in both PP populations, both mITT populations, and the ITT population.

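### The non-inferiority test for Secondary Objective 6 gives drop-outs a fixed outcome that is the same in both arms; if they would have responded like completers, this shrinks a true deficit, and no sensitivity analysis against the margin is given in the supplied documents

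*Combined protocol and SAP*

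**What the plan says.** - **Test and population.** Table 11 (Section 11.4.4.2) declares non-inferiority if the 95% confidence interval for the difference in Day 22 response excludes 0.05 in favour of placebo. It names the ITT population only, which Section 11.4.1 defines so: "This efficacy analysis population includes all randomized subjects".
- **Drop-outs.** The rule appears only in the sample-size text, Section 11.2.1: "Subjects who drop-out before Day 22 will be imputed as non-responders for cocci-positive subjects, and as responders for cocci-negative subjects". The plan expects about 80% of enrolment to be cocci-negative, so most drop-outs would be scored as responders.
- **Objective wording.** Section 3.1.2 describes the SO 6 subjects as all randomized, "regardless of coccidioidomycosis pneumonia status or adherence with study intervention, with baseline and follow-up FLEET-CAP scores". The Protocol Summary and Table 11 repeat this.
- **Sensitivity analyses.** Section 11.4.4.1 says: "Sensitivity analyses, which will assess the impact of drop-out, censoring mechanisms, and analysis methods on the primary analysis, may be performed". The same section commits to further analyses, including one in the all-randomized per-protocol population, and cross-refers to SO 6.
- **Further detail.** On the secondary analyses, Section 11.4.4.2 says: "Details of the analyses will be described in the separate statistical analysis plan document". That document is not among those supplied.
- **Data on those who leave.** Section 7.4.1 includes "Complete symptom Assessment including FLEET CAP Score" and serology at early termination. Section 5.3.4 says of that visit: "Subjects will be encouraged to complete the Early Termination Visit".

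**The concern.** A non-inferiority test has to show that fluconazole is not worse by 5 points. Giving lost subjects in both arms the same value makes the arms look more alike, which favours that conclusion. SO 6 asks whether empiric fluconazole does harm to response across all pneumonia patients, most of whom are expected not to have coccidioidomycosis. A positive result should therefore rest on observed outcomes and not on the scoring of drop-outs.

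Two gaps add to this. First, the imputed value depends on cocci status, but case criteria 2 to 4 in Section 3.2.1 need a sample after Day 1. A subject who is seronegative on Day 1, leaves early and skips the termination visit cannot be classified, and no default is given. Second, the wording about baseline and follow-up scores can be read as limiting SO 6 to scored subjects, in which case there is nothing to impute. Section 11.2.1, the ITT definition and the population named in Table 11 say otherwise.

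**Working it through.** **Inputs.** From Section 11.2.1: 20% cocci-positive; response 0.20 (placebo) and 0.40 (fluconazole) if cocci-positive, 0.70 in both arms if cocci-negative; 20% loss in both arms and both strata, as used in the SO 6 formula; margin 0.05; two-sided level 0.05, so 2.5% on the non-inferiority side. From Section 5.3.1: 1:1 allocation, so 500 or 625 per arm.

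**Formula.** P(non-inferior) = Φ[(pF − pP + 0.05)/SE − 1.96], with SE = √[pP(1 − pP)/n + pF(1 − pF)/n].

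**1. The plan's own figures.** With pP = 0.64 and pF = 0.672:
- n = 500: SE = 0.03003; 0.082/0.03003 = 2.731; Φ(0.771) = 78.0%.
- n = 625: SE = 0.02686; 0.082/0.02686 = 3.053; Φ(1.093) = 86.3%.

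Both match the stated 78% and 86%.

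**2. A true deficit exactly at the margin.** Placebo without loss is 0.2×0.2 + 0.8×0.7 = 0.60, so fluconazole is set to 0.55. If drop-outs would respond like completers in their arm, the rule turns a true rate p with loss d into (1 − d)p + 0.8d. At d = 0.20:
- placebo: 0.8×0.60 + 0.16 = 0.64
- fluconazole: 0.8×0.55 + 0.16 = 0.60

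The deficit shrinks from 0.05 to 0.04, whichever stratum carries it. At n = 500, SE = 0.03067 and 0.01/0.03067 = 0.326, so Φ(−1.634) = 5.1%. A simulation of 1,000,000 trials gave 5.06%. At n = 625 the result is 5.5%.

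| Equal loss (n = 500) | Observed rates | False non-inferiority |
|---|---|---|
| 0% | 0.60 vs 0.55 | 2.5% |
| 10% | 0.62 vs 0.575 | 3.6% |
| 15% | 0.63 vs 0.5875 | 4.3% |
| 20% | 0.64 vs 0.60 | 5.1% |

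**3. Is the responder direction the cause?** Scoring all drop-outs as non-responders gives 0.48 vs 0.44: SE = 0.03150, 0.01/0.03150 = 0.317, error 5.0%. At equal loss the direction hardly matters.

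**4. Drop-outs carrying only part of the deficit.** Let D be the completers' deficit and k the share of it carried by drop-outs, with the overall deficit held at 0.05: 0.8D + 0.2kD = 0.05. The deficit seen after imputation is 0.8D.

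| k | 0.8D | Error (n = 500) |
|---|---|---|
| 0 | 0.0500 | 2.5% |
| 0.5 | 0.0444 | 3.8% |
| 1 | 0.0400 | 5.1% |

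**5. Unequal loss.** The documents give no arm-specific rates, so these are assumptions (n = 500).
- Placebo 20%, fluconazole 22%: 0.78×0.55 + 0.176 = 0.605 vs 0.64; error 7.1%.
- Placebo 20%, fluconazole 25%: 0.75×0.55 + 0.20 = 0.6125 vs 0.64; error 11.0%.
- Placebo 25%, fluconazole 20%: 0.60 vs 0.75×0.60 + 0.20 = 0.65; error 2.5%. Power at the plan's 0.672 falls to Φ(0.072/0.02993 − 1.96) = 67%.

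**6. Power without the fixed values.** With 20% loss, scored subjects number 400 or 500 per arm, at true rates 0.60 and 0.64 (0.2×0.4 + 0.8×0.7). At 400: SE = 0.03429, 0.09/0.03429 = 2.625, power 74.7%. At 500: 83.5%. Error at 0.60 vs 0.55 is 2.5%. Simulated by-arm imputation under random loss, without any early-termination score, gave power of 75.1% and 84.4%.

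**The case against.** **Other analyses already planned.** Section 11.4.4.1 commits to an all-randomized per-protocol analysis and cross-refers to SO 6. That population requires Day 22 serology, so it largely leaves out subjects lost earlier and is close to a completers' analysis. The same section codes subjects without a Day 22 response as failures, and Table 11 repeats the primary analysis in ITT, which could amount to all-non-responder scoring. This stands in part. A reader might infer that the plan offers no other view of drop-out, and that would be too strong. But these are tests of difference, and Table 11 applies the 0.05 margin in ITT only.

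**The separate analysis plan may fill the gap.** It may. The absence can be stated only for the documents supplied.

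**The assigned outcome could be the endpoint.** If so, the true difference is 4 points and nothing is inflated. If SO 6 covers scored subjects only, error is 2.5%. Both points are correct, but the documents do not state the first and contradict themselves on the second.

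**Loss may be small or harmless.** Subjects taken off treatment continue to be followed (Section 5.3.3.1), rescue subjects are invited to stay (Section 6.7), and outcome data are sought from those leaving (Section 5.3.4). This weakens the link between stopping drug and missing Day 22, but the plan itself still assumes 20% loss.

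**Stronger readings.** A reader might infer that scoring cocci-negative drop-outs as responders is itself what inflates error. At equal loss it is not (5.0% versus 5.1%). A reader might also infer much larger errors from wide arm imbalance or outcome-related loss; the documents give no rates that would support such figures.

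**Conclusion.** The concern holds within limits. Under the stated rule, with the plan's equal 20% loss, false non-inferiority for SO 6 at a true 5-point deficit is about 5.1% at 1,000 subjects and 5.5% at 1,250, against 2.5%. This rests on two assumptions: that the endpoint is Day 22 response itself, and that drop-outs would respond like completers in their arm. The inflation falls to 3.8% if drop-outs carry half the completers' deficit and vanishes if they carry none. Unequal loss can move the result either way: more loss on fluconazole raises error, and more loss on placebo lowers error and power. A reader might infer that the trial's main conclusion is at risk. It is not: the primary analysis, its sample size and the futility rules do not use this imputation. The point should be fixed because the test leans towards its own conclusion and the remedy needs only analysis text.

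**What to change.** - **Main SO 6 analysis.** Replace the fixed values with multiple imputation of Day 22 response within arm, using baseline FLEET CAP and available serology as covariates.
- **Tipping point.** Worsen the imputed fluconazole outcomes until non-inferiority at 0.05 is lost. At the plan's rates and 20% loss, the expected lower limit reaches −0.05 when imputed response is about (0.09 − 1.96×0.03429)/0.20 = 11 points worse at 1,000 subjects, and about 15 points worse at 1,250.
- **Supporting analyses.** Apply the same margin to scored subjects or to the all-randomized per-protocol population. Keep the current rule and all-non-responder scoring as sensitivity analyses.
- **Early-termination score.** Its use is optional and needs a stated assumption. Section 8.1 says: "The FLEET CAP score will be completed on Days 1, 22, 29, and 43". Completers therefore have no score between Day 1 and Day 22 from which to estimate the link to Day 22 response.
- **Text.** State how drop-outs with undetermined cocci status are handled. Reconcile the wording on baseline and follow-up scores (Protocol Summary, Section 3.1.2, Table 11) with the all-randomized ITT population and the imputation (Sections 11.2.1 and 11.4.1, Table 11).
- **Power.** Restate as about 75% at 1,000 and 84% at 1,250.

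**Cost.** About 3 points of stated power and a little more analysis work; no new data. Multiple imputation assumes that missingness is explained by the observed data, which is why the tipping-point analysis must go with it.
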